**7.6.2 6 Months**

The following assessments will be conducted by telephone or office visit at 6 months (+30 days):

**Systems:**

- Medications: Antithrombotics only
- Adverse Events

### **7.6.3 Years 1, 3 and 5**

The following assessments will be conducted at years 1, 3 and 5 (+ 45 days):

#### **Systems:**

- Physical assessment (weight, blood pressure and heart rate only)
- Medications: Antithrombotics only
- Adverse Events

#### **Cardiopulmonary:**

- NYHA functional class

### **7.6.4 Years 2 and 4**

The following assessments will be conducted by telephone or office visit at years 2 and 4 (+ 45 days):

#### **Systems:**

- Medications: Antithrombotics only
- Adverse Events

### **7.7 Imaging Assessments**

Imaging performed during the course of the study should follow the CT Reference Document and the Echo Manual of Operations, except for the limited TTE performed post-procedure, which is only performed to assess PVL.

### **7.8 Neurological Assessments**

Every effort should be made to have a neurologist (or neurology fellow) perform the mRS assessment. If it is not possible to have the neurologist/fellow perform the assessments within the protocol-specified visit window, a certified study team member may perform them.

Following the procedure, all subjects should be assessed to determine if there is evidence of neurological impairment. For all subjects diagnosed with a new stroke after the procedure start, a follow-up mRS assessment should be performed 90 days ( $\pm$  30 days) after stroke onset to assess stroke disability (visit or phone assessment is acceptable). If the 90-day post-stroke assessment is scheduled to occur within 30 days of a protocol-specified visit, the mRS does not need to be repeated.

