**Neurological:**

- Modified Rankin Scale (mRS)

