## **7.4 Post-procedure**

The post-procedure time period is defined as the 48 hours after the subject exits the procedure room. The following will be assessed during the post-procedure time period:

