## **7.5 Discharge**

Discharge is the actual date and time the subject is discharged. For subjects discharged within 48 hours of exiting the procedure room, it is not required to repeat tests collected during the Post-Procedure period that are also required for the discharge visit. If the subject was discharged over a weekend or holiday, the discharge assessments may be completed on the last weekday prior to discharge.

The following assessments will be conducted within 24 hours of the date and time of discharge.

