**7.6 Follow-up**

The day of the procedure is considered Day 0 and will be used to schedule all subsequent visits and calculate visit windows. Six months is defined as 180 days; one year is defined as 365 days.

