**7.6.1 30 Days**

The following assessments will be conducted at 30 days (+7 days):

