**Table 3: Schedule of Assessments**

	Screening	Procedure	Post-Procedure	Discharge	30 Days	6 Months o,p	1, 3, 5 Years p	2, 4 Years o,p
Visit Window (days)	- 30 a		+ 2 n		+ 7	+ 30	+ 45	+ 45
Informed Consent	X							
Medical History	X							
Physical Assessment	X			X	X		X	
Medications: Antithrombotics	X	X	X	X	X	X	X	X
Adverse Events		X	X	X	X	X	X	X
STS Risk Score	X							
EuroSCORE II	X							
NYHA Functional Class	X			X	X		X	
12-lead ECG	X		X					
TTE	X b			X	X			
Cardiac CTA	X c							
Iliofemoral CTA	X c							
Assessment of CAD	X c,d							
Assessment of valve placement			X					
Assessment of PVL			X m					
Pulmonary Function Test	X e							
SYNTAX Score	X f							
mRS g	X							
WBC, Hgb, Platelet Count	X		X	X				
PT or INR	X		X	X				
CK and/or Troponins	X h							
eGFR	X							
Creatinine	X		X	X				
Albumin, Total Bilirubin	X							
AST/ALT	X i							
Pregnancy test	X j							
Frailty Index	X k							
Case Review	X l							
Valve Implant Procedure		X						

- a. Screening assessments will be completed within 30 days prior to valve implant procedure, unless otherwise noted.
- b. Must be performed within 90 days prior to the valve implant procedure.
- c. Must be performed within 1 year prior to the valve implant procedure.
- d. Assessment of severity of CAD may be performed by CTA or coronary angiography. If CTA shows evidence or high likelihood of obstructive CAD or if the CTA is non-diagnostic, coronary angiography must be performed to assess the need for intervention.
- e. Only for subjects with a history of lung disease.
- f. Only for subjects with significant native CAD.
- g. Every effort should be made to have a neurologist (or neurology fellow) perform the assessment. If it is not possible to have the neurologist/fellow perform the assessments within the protocol-specified visit window, a certified study team member may perform them. Following the procedure, all subjects should be assessed to determine if there is evidence of neurological impairment. For all subjects diagnosed with a new stroke after the procedure start, a follow-up mRS assessment should be performed 90 days ( $\pm$  30 days) after stroke onset to assess stroke disability (visit or phone assessment is acceptable).
- h. Required  $\leq$  72 hours before the valve implant procedure.

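### Section 7.8 waives the 90-day post-stroke mRS near a protocol visit, although no visit after Screening includes an mRS and Table 3 footnote g has no such waiver

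*Combined protocol and SAP*

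**What the plan says.** Section 7.8 and Table 3 footnote g share the same core instruction. In the footnote's words: "For all subjects diagnosed with a new stroke after the procedure start, a follow-up mRS assessment should be performed 90 days", with a tolerance of ± 30 days after onset, by visit or telephone. Section 7.8 then adds a sentence that the footnote lacks: "If the 90-day post-stroke assessment is scheduled to occur within 30 days of a protocol-specified visit, the mRS does not need to be repeated".

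The mRS is scheduled once, at Screening (Section 7.2, Neurological). It does not appear in the assessment lists for the procedure (7.3), post-procedure (7.4), discharge (7.5), 30 days (7.6.1), 6 months (7.6.2), years 1, 3 and 5 (7.6.3) or years 2 and 4 (7.6.4). The 6-month, year-2 and year-4 contacts collect only antithrombotics and adverse events. The mRS row of Table 3 is marked at Screening only.

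Appendix B classes a stroke as disabling when the mRS is at least 2 at 90 days, or at the last clinical visit with usable data, and has risen by at least one category from the pre-stroke baseline.

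**The concern.** A waiver of this kind makes sense when the nearby visit brings its own mRS, so that a second one would duplicate it. Here no later visit does. A site that follows Section 7.8 to the letter can drop the post-stroke mRS because a visit is close, and then attend a visit at which no mRS is asked for. A site that follows footnote g does the assessment.

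At stake is the severity grade of a non-fatal stroke. The fallback in Appendix B to the last usable visit does not close the gap, because the schedule places no mRS after the stroke. If someone carried the Screening score forward under that fallback, the comparison would be baseline against itself. It would show no increase, and the stroke would be graded non-disabling by default. Fatal strokes are not exposed, since the scale has its own score for death (6).

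**Working it through.** **Text comparison**

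| Place | 90-day post-stroke mRS required? | Waiver near a visit? | mRS scheduled at that visit? |
|---|---|---|---|
| Section 7.8 | Yes, all new strokes | Yes | – |
| Table 3 footnote g | Yes, all new strokes | No | – |
| Section 7.2, Screening | – | – | Yes |
| Sections 7.3 to 7.6.4 | – | – | No |

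Section 7.8 also asks that all subjects be checked for neurological impairment after the procedure, but names no scale and no time point. That does not supply a post-stroke mRS.

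**How much of follow-up the waiver can reach**

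The plan gives no figure on this point to reproduce. The inputs are its own visit days. Section 7.6 sets the procedure as day 0 and states: "Six months is defined as 180 days; one year is defined as 365 days". The follow-up visits are therefore nominally on days v = 30, 180, 365, 730, 1095, 1460 and 1825. Let s be the day of stroke onset, from 0 to 1825 (1,826 possible days), with the mRS targeted at day s + 90.

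The waiver applies when |s + 90 − v| ≤ 30, that is, when v − 120 ≤ s ≤ v − 60.

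| Visit day v | Onset days covered | Count |
|---|---|---|
| 30 | −90 to −30 | 0 |
| 180 | 60–120 | 61 |
| 365 | 245–305 | 61 |
| 730 | 610–670 | 61 |
| 1095 | 975–1035 | 61 |
| 1460 | 1340–1400 | 61 |
| 1825 | 1705–1765 | 61 |

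Total: 6 × 61 = 366, and 366 / 1,826 = 20.0%. No onset before day 60 is covered. Discharge does not change this: s + 90 is at least 90, so it can lie within 30 days of discharge only if the index stay lasts to day 60 or later.

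**Effect of the visit windows** (+7 days at 30 days, +30 at 6 months, +45 at the yearly visits)

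A subject attends each visit on one date. If the visit takes place k days after its nominal day, its band moves k days later and still holds 61 onset days. The bands stay separate and inside follow-up: the latest possible year-5 visit, day 1825 + 45 = 1870, covers days 1750–1810. The 30-day visit at its latest, day 37, covers −83 to −23, so still none. The count for any one subject is 366 wherever the visits fall.

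**Dependence on the day-90 target**

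The ± 30-day tolerance allows other dates. For example, a day-0 stroke with its mRS set for day 60 lies exactly 30 days from the day-30 visit. The result that nothing before day 60 is covered therefore assumes a day-90 target.

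**The case against.** The strongest answer is linguistic. An assessment can be *repeated* only if it has been done. With no mRS at the nearby visit there is nothing to repeat, the waiver never operates, and the 90-day requirement stands in full. Section 7.8 also speaks of mRS assessments falling in visit windows, which fits a sentence meant only to avoid duplicates. This reading is reasonable, and under it no data are lost. It does not remove the point, because the stated condition is nearness to a visit and a site could apply it as written.

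Second, Section 7.9 says that Table 3 summarizes the assessments. A summary note that leaves out an exception is incomplete and need not countermand the body text. That is fair: the difference between the two places is a mismatch to reconcile, not proof that one overrides the other.

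Third, the Appendix B fallback would accept an unscheduled post-stroke mRS. It would, if a site happened to record one, but the plan does not ask for one.

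Fourth, no planned analysis depends on the grade. Section 5 puts stroke in neither the primary nor the secondary endpoints, and Section 10.3 plans descriptive statistics and Kaplan-Meier estimates without naming disabling stroke. This stands and limits the weight of the point.

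**Conclusion.** The point holds as a minor inconsistency. On a literal reading, Section 7.8 permits omission of the only planned post-stroke mRS, which footnote g requires for every new stroke. A non-fatal stroke could then go without a disability grade. The loss is possible, not certain. With a day-90 target the waiver reaches 366 of 1,826 onset days (20%), none before day 60. The effect is confined to descriptive safety reporting of stroke severity; the primary and secondary endpoints, the 90% success criterion and the sample size are untouched.

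Three stronger inferences are tempting and not supported:

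- **That about a fifth of strokes would go ungraded.** The 20% is a share of calendar days. The documents give no timing of strokes, and onset need not be spread evenly.
- **That a number of affected subjects can be derived from the disabling-stroke rates in Section 1.2.** Those rates belong to earlier valves, do not separate out fatal strokes, and leave out non-disabling ones. The group at issue is all non-fatal strokes with this device, for which the documents give no rate.
- **That the visit windows raise the share.** Pooling every onset day that some permitted visit date could reach gives 91 + 5 × 106 = 621 days (34%). That is a union over alternative dates, and no single subject's visits cover it.

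**What to change.** Delete the waiver sentence from Section 7.8, so that it agrees with Table 3 footnote g. This is safe under either reading: it keeps the score if the sentence would have been applied literally, and removes a redundant line if not.

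If the sponsor wants to keep some relief from duplicate assessments, the sentence can be limited to cases where a post-stroke mRS has actually been recorded within 90 ± 30 days of onset, with the same text in footnote g. The limit on timing is needed. An mRS scheduled 60 to 120 days after onset, with a visit up to 30 days away, allows a visit 30 to 150 days after onset. For example, with onset on day 40 and the mRS set for day 155, the day-180 visit is 25 days from the mRS date but 140 days after onset.

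The cost is one sentence in Section 7.8 and, for the second option, one in footnote g. Section 12.6 requires a written amendment, IRB/EC approval at each site (up to 8), any required training and the sponsor's written approval, so the change is best bundled with the next amendment. For subjects it means at most one additional mRS per affected stroke, which may be done by telephone.

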## 7.9 Subject Disposition

The following categories of subject disposition have been defined for this trial:

**Enrolled**: Subjects will be considered enrolled once the ICF is signed and dated.

**Discontinued**: Enrolled subjects will be considered discontinued when they exit the study prior to completing all required follow-up. Potential reasons include but are not limited to:

- **Study Procedure Never Started**: Subjects considered enrolled that do not meet pre-procedure eligibility criteria will be exited from the study.
- **Procedure Started but Study Device Never Implanted**: Subjects in whom the procedure was started but did not receive a study valve will be followed for 30 days or until resolution of any adverse events related to the valve implant procedure and then exited from the study.
- **Study Device Explanted**: Subjects who have a surgical reintervention where the study valve is explanted will be followed for 30 days post-reintervention or until resolution of any adverse events related to the procedure and then exited from the study.

Subjects that have a valvuloplasty or valve-in-valve procedure will continue to be followed for the duration of the study.

If a subject discontinues, all attempts should be made to have the subject come into the clinic for an exit visit. An exit form indicating the reason for discontinuation will be completed. Subjects who discontinue will not be replaced.

**Completed**: Enrolled subjects will be considered to have completed the study when all required follow-up has been performed.

**Table 3** summarizes the subject assessments at each time point.

**Table 3: Schedule of Assessments**

	Screening	Procedure	Post-Procedure	Discharge	30 Days	6 Months o,p	1, 3, 5 Years p	2, 4 Years o,p
Visit Window (days)	- 30 a		+ 2 n		+ 7	+ 30	+ 45	+ 45
Informed Consent	X							
Medical History	X							
Physical Assessment	X			X	X		X	
Medications: Antithrombotics	X	X	X	X	X	X	X	X
Adverse Events		X	X	X	X	X	X	X
STS Risk Score	X							
EuroSCORE II	X							
NYHA Functional Class	X			X	X		X	
12-lead ECG	X		X					
TTE	X b			X	X			
Cardiac CTA	X c							
Iliofemoral CTA	X c							
Assessment of CAD	X c,d							
Assessment of valve placement			X					
Assessment of PVL			X m					
Pulmonary Function Test	X e							
SYNTAX Score	X f							
mRS g	X							
WBC, Hgb, Platelet Count	X		X	X				
PT or INR	X		X	X				
CK and/or Troponins	X h							
eGFR	X							
Creatinine	X		X	X				
Albumin, Total Bilirubin	X							
AST/ALT	X i							
Pregnancy test	X j							
Frailty Index	X k							
Case Review	X l							
Valve Implant Procedure		X						

- a. Screening assessments will be completed within 30 days prior to valve implant procedure, unless otherwise noted.
- b. Must be performed within 90 days prior to the valve implant procedure.
- c. Must be performed within 1 year prior to the valve implant procedure.
- d. Assessment of severity of CAD may be performed by CTA or coronary angiography. If CTA shows evidence or high likelihood of obstructive CAD or if the CTA is non-diagnostic, coronary angiography must be performed to assess the need for intervention.
- e. Only for subjects with a history of lung disease.
- f. Only for subjects with significant native CAD.
- g. Every effort should be made to have a neurologist (or neurology fellow) perform the assessment. If it is not possible to have the neurologist/fellow perform the assessments within the protocol-specified visit window, a certified study team member may perform them. Following the procedure, all subjects should be assessed to determine if there is evidence of neurological impairment. For all subjects diagnosed with a new stroke after the procedure start, a follow-up mRS assessment should be performed 90 days ( $\pm$  30 days) after stroke onset to assess stroke disability (visit or phone assessment is acceptable).
- h. Required  $\leq$  72 hours before the valve implant procedure.
- i. Only required for subjects with chronic liver disease.
- j. Only for female subjects of childbearing potential (urine or serum)
- k. Includes activities of daily living, 5 meter walk test, grip strength and albumin.
- l. Case Review will be completed when all screening procedures have been completed, all inclusion/exclusion criteria have been fundamentally confirmed and the site is ready to present a case.
- m. By TEE or Limited TTE AND Aortogram
- n. Post-procedure time period is defined as the 48 hours after the subject exits the procedure room.
- o. Can be done by telephone or office visit.
- p. Six months is defined as 180 days; one year is defined as 365 days.

## 8 ADVERSE EVENTS

### 8.1 Adverse Event Definitions

An **Adverse Event** (AE) is any untoward medical occurrence, unintended disease or injury or untoward clinical signs (including abnormal laboratory findings) in subjects, users or other persons, whether or not related to the study device. For users or other persons, this definition is restricted to events related to the study device.

AEs may be volunteered by subjects, elicited or collected via observation by the Investigator or designee, or discovered by review of clinical records by Edwards Safety team or Edwards Monitoring team. Subjects will be instructed to contact the Investigator and/or study coordinator if any significant AEs occur between study visits.

A **Serious Adverse Event** (SAE) is any adverse event that:

- Led to death;
- Led to serious deterioration in the health of the subject that either resulted in:
  - a life-threatening illness or injury;
  - a permanent impairment of a body structure or a body function;
  - in-patient or prolonged hospitalization;
  - medical or surgical intervention to prevent life-threatening illness or injury or permanent impairment to body structure or a body function;
- Led to fetal distress, fetal death or congenital abnormality or birth defect;
- Significant medical event: Important medical events that do not meet the above criteria may still be considered an SAE if they seriously jeopardize the subject and require immediate medical or surgical intervention to prevent one of the aforementioned outcomes.

**NOTE 1:** Planned hospitalization for pre-existing condition, or a procedure required by the Clinical Investigation Plan, without a serious deterioration in health, is not considered a serious adverse event.

**NOTE 2:** Permanent impairment of a body structure or a body function - An AE, which results in a substantial disruption of a person's ability to conduct normal life functions. This does not pertain to minor events, but to serious events which result in a significant, persistent or permanent change, impairment, damage or disruption in the subject's body function/structure, physical activities and/or quality of life.

**NOTE 3:** Life-threatening – an event in which the subject was at risk of death at the time of the event; it does not refer to an event which hypothetically might have caused death if it were more severe.

**Adverse Device Effects (ADE) and Serious Adverse Device Effects (SADE)** are AEs related to the use of a medical device.

**NOTE 1:** This includes any AE resulting from insufficiencies or inadequacies in the IFU, the deployment,

the implantation, the installation, the operation or any malfunction of the medical device.

**NOTE 2:** This includes any event that is a result of a user error or intentional abnormal use of the medical device.

**Anticipated AE** means an effect which by its nature, incidence, severity or outcome has been previously identified in the risk analysis report. The potential AEs associated with the procedures involved and study devices are listed in the current IFU.

**Unanticipated Serious Adverse Device Effect (USADE)** is defined as any SADE which by its nature, incidence, severity or outcome has not been identified in the current version of the risk analysis report or IFU.

**Device Deficiency** is defined as an inadequacy of a medical device related to its identity, quality, durability, reliability, safety or performance. This may include malfunctions, use error or inadequacy in the information supplied by the manufacturer.

A malfunction or deterioration is defined as the failure of a device to perform in accordance with its intended purpose when used in accordance with the manufacturer's instructions. The intended performance of a device refers to the intended use for which the device is labeled or marketed.

Reporting conventions for device deficiencies that could result in an SAE are the same as those for an actual SAE.

## **8.2      Investigator Assessment of AEs**

For each AE, the Investigator will determine whether the event is related to the device and/or the implant procedure, whether it was anticipated or not anticipated (based on the list of potential risks provided in the IFU) and whether the event meets the definition of an SAE or USADE.

The causal relationship of the event to the device and the implant procedure will be categorized as follows:

- 1) Not related: relationship to the device or procedures can be excluded when there is no temporal relationship, the event is not a known adverse effect of similar devices or procedures, it is not clinically plausible, or the event can be attributed to another cause.
- 2) Unlikely: the relationship with the use of the device seems not relevant and/or the event can be reasonably explained by another cause, but additional information may be obtained.
- 3) Possible: the relationship with the use of the device is weak but cannot be ruled out completely. Alternative causes are also possible (e.g. an underlying or concurrent illness/ clinical condition or/and an effect of another device, drug or treatment). Cases where relatedness cannot be assessed or no information has been obtained should also be classified as possible.
- 4) Probable: the relationship with the use of the device seems relevant and/or the event cannot

be reasonably explained by another cause, but additional information may be obtained.

5) Causal relationship: the event is associated with the device or with procedures beyond reasonable doubt when there is a temporal relationship, the event is a known adverse effect of similar devices or procedures, it is clinically plausible, or the event cannot be attributed to another cause.

